4.5.16.7 Monitoring and Oversight

RBR samples will be tracked in a manner consistent with Good Clinical Practice by a quality-controlled, auditable, and appropriately validated laboratory information management system, to ensure compliance with data confidentiality as well as adherence to authorized use of samples as specified in this protocol and in the Informed Consent Form. Sponsor monitors and auditors will have direct access to appropriate parts of records relating to patient participation in the RBR for the purposes of verifying the data provided to the Sponsor. The site will permit monitoring, audits, IRB/EC review, and health authority inspections by providing direct access to source data and documents related to the RBR samples.

4.6 TREATMENT, PATIENT, STUDY, AND SITE DISCONTINUATION

It should be noted that study treatment discontinuation and patient discontinuation from the study are managed differently, as follows:

- *Patients who discontinue study treatment will continue with study visits and assessments (without continuing to receive study drug treatment)*
- *Patients who discontinue from the study will be invited to enroll in the OLE study for long-term follow-up of survival data, if they do not wish to continue with study drug treatment and other assessments and visits.*

4.6.1 Study Treatment Discontinuation

Patients must permanently discontinue study treatment if they experience any of the following:

- Any medical condition that the investigator or Sponsor determines may jeopardize the patient's safety if he or she continues to receive study treatment
- Investigator or Sponsor determination that treatment discontinuation is in the best interest of the patient
- Pregnancy
- Anaphylaxis or serious hypersensitivity reaction
- Grade 4 IRR or two Grade 3 IRRs
- Lung transplant

The primary reason for study treatment discontinuation should be documented on the appropriate eCRF. Patients who discontinue study treatment prematurely will not be replaced.

If a patient discontinues study drug treatment prematurely for any reason, the patient will be encouraged to complete all planned study visits *and assessments (except for IMP administration)* through to Week 52. If unable to return for the remaining protocol visits *through to week 52*, patients will return to the clinic for a treatment discontinuation visit 4 weeks after the final dose of study drug (see [Appendix 1](#) for additional details). Every effort should be made to collect spirometry, 6MWD, safety, and survival data at *the* time of the Week 52 or treatment discontinuation visit.

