3.1.1 Overall Study Design and Plan

This Phase III, randomized, double-blind, placebo-controlled, pivotal study is designed to confirm the efficacy and safety of PRM-151 in the treatment of patients with IPF during a 52-week period. At the end of this 52-week period, patients will be invited to enroll in *an* open-label extension study (Study WA42294) to receive treatment with PRM-151. Patients who do not enroll in the OLE study will be followed up for an additional 4 weeks (to Week 56, for safety monitoring).

The OLE study will provide patients with further study assessments and PRM-151 treatment on an ongoing basis. However, the OLE study will also consist of a long-term survival cohort, in which patients who do not want further study assessments or treatment can enroll (for long-term collection of survival data only).

[Figure 1](#) presents an overview of the study design. A schedule of activities is provided in [Appendix 1](#).

Figure 1 Study Schema

OLE = open-label extension; Q4W = once every 4 weeks.

^a Patients will have a final assessment visit at Week 52 (4 weeks after the final study drug infusion). For patients enrolling in the OLE study, this will also be their end of study visit.

^b Patients who do not enroll in the OLE study will have their final assessment visit at Week 52, followed by an end of study visit at Week 56 (8 weeks after the final study drug infusion).

Patients meeting the eligibility criteria for the study will be randomized to PRM-151 10 mg/kg Q4W or placebo. Efficacy will be evaluated through assessment of functional capacity as measured by FVC, 6MWD, other PFTs, and assessment of patients with respiratory events leading to hospitalizations, progression of disease, acute IPF exacerbations.

Patient reported outcomes (PROs) will be assessed using the SGRQ, UCSD-SOBQ, and EQ-5D-5L.

Dyspnea, fatigue, and SpO₂ will be assessed based on measurements taken during the 6MWT. For patients who require a HRCT scan during the screening period, an additional chest HRCT scan will be performed at Week 52. Patients who do not require a HRCT scan during the screening period (i.e., they already have a historic HRCT scan of acceptable quality performed within 12 months prior to screening) will not be required to perform a scan at Week 52.

Treated patients will be followed until the end of the 52-week study period unless the patient withdraws consent for follow-up or dies.

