To avoid underestimating the power of the study and to enable the opportunity to explore the efficacy in relevant patient subgroups including baseline concomitant IPF medication use, smaller standardized effect-sizes than observed in study PRM-151-202 at Week 28 of 0.25 for FVC mL and FVC % predicted and 0.30 for 6MWD were used for the calculations. In addition, to investigate the impact of increased variability for studies of longer duration, the power for this calculated sample size was assessed in the following way: (a) using the placebo-controlled treatment differences observed at Week 28 as estimates for the Week 52 treatment effects and (b) using the Week 52 standard deviations for the initially randomized PRM-151 arm from study PRM-151-202, as

estimates for the Week 52 common standard deviations. This was performed in order to confirm that the nominal power is at least 80% under these assumptions.

With a total of 658 patients (329 in each arm), the nominal power to detect a standardized effect size of 0.25 for FVC mL and FVC % predicted, using a two-sided type I error level of 0.05 is 0.89 and the nominal power to detect a standardized effect size of 0.30 on 6MWD using a two-sided type I error level of 0.05 is 0.97.

With a total of 658 patients (329 in each arm), the nominal power to detect an effect of 114.6 mL on FVC mL with common standard deviation of 403.5 (standardized effect size of 0.28) using a two-sided type I error of 0.05 is 0.95. The nominal power to detect an effect of 33.5 meters on 6MWD with common standard deviation of 82.3 (standardized effect size of 0.41) using a two-sided type I error level of 0.05 is >0.99. For FVC % predicted, the nominal power to detect an effect of 2.80% with common standard deviation of 8.77 (standardized effect size of 0.32) using a two-sided type I error of 0.05 is 0.98.

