6.2.1.1 Robustness of Power and Sample-Size Calculations

In [Table 7](#), power calculations for alternative values of the effect-sizes of the *first* three endpoints in the fixed-*sequence* testing are provided.

With the planned sample size of 658 patients, a standardized effect-size of 0.220 on FVC, both mL and % predicted (corresponding to absolute between group differences of 89 mL and 1.92%, respectively) will be detected with a power of 80%.

For 6MWD, the study has a high power (0.973) to detect an absolute between group difference of 25 m (considered the minimal clinically relevant difference), corresponding to a standardized effect-size of 0.30. A smaller effect-size of 0.25, corresponding to an absolute difference of 20.8 m will be detected with a power of 90%.

Table 7 Results of Power Calculations for Different Effect-Sizes and N=658 Patients

	alpha	Hypothesized absolute difference	Power with N=658 patients
FVC (mL) H0: difference = 0	0.05 2-sided	114.6	0.953
		107.0	0.925
		102.0	0.899
		95.0	0.854
		89.0	0.806
6MWD (meters) H0: difference = 0	0.05 2-sided	33.5	>0.999
		27.5	0.990
		25.0	0.973
		23.0	0.947
		20.8	0.899
		18.0	0.800
FVC (% predicted) H0: difference = 0	0.05 2-sided	2.80	0.983
		2.45	0.947
		2.33	0.925
		2.22	0.900
		2.05	0.849
		1.92	0.800

Standard deviation of 403.5 mL (FVC mL), 82.3 m (6MWD) and 8.77 (FVC %predicted) based on Week 52 standard errors from the MMRM model in patients who were initially randomized to PRM-151 in Study PRM-151-202. 6MWD = 6-minute walk distance; FVC = forced vital capacity.

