Appendix 1: Schedule of Activities

ADA=anti-drug antibody; AE=adverse event; Discon.=discontinuation; DLCO=diffusing capacity for carbon monoxide; eCRF=electronic Case Report Form; EQ-5D-5L=EuroQol 5-Dimension, 5-Level Questionnaire; HRCT=high-resolution computed tomography; IPF=idiopathic pulmonary fibrosis; OLE=open-label extension; PCR=polymerase chain reaction; PD=pharmacodynamic; PK=pharmacokinetic; SGRQ=St. George Respiratory Questionnaire; SAE=serious adverse event; SARS-CoV-2=severe acute respiratory syndrome coronavirus 2; TB=tuberculosis; Treat.=treatment, UCSD-SOBQ=University of California, San Diego-Shortness of Breath Questionnaire.

- ^a Screening period is up to 4 weeks. Eligible patients can be randomized as soon as their screening assessments have been completed and all eligibility criteria have been confirmed. Randomization must occur prior to any baseline assessments being conducted on Visit 2.
- ^b Patients will have their final safety and efficacy assessments, including HRCT if applicable, at Week 52.
- ^c Patients not enrolling in the OLE study will return for an end-of-study visit at Week 56.
- ^d Treatment discontinuation visit should occur 4 weeks after final dose of study drug. Study discontinuation visit should occur 4 weeks after the treatment discontinuation visit (8 weeks after the final dose of study drug).
- ^e To allow for flexibility around weekends, holidays, and so on, the loading dose visits may occur over a time span of up to 8 days, with a minimum of 1 full calendar day between administration of doses (patients must not be dosed on consecutive days). In case one or more loading doses have been missed or delayed beyond the 8-day loading phase window, loading doses should be administered again at the next scheduled visit. No loading doses should be administered outside of the 8-day loading phase window.
- ^f Patients who discontinue study drug early will have \pm 2-week window to complete study visits.
- ^g Testing for active or latent TB should be conducted with an interferon gamma release assay during screening. Patients who have completed treatment for active or latent tuberculosis within 6 months prior to screening, and have no evidence of recurrent disease, do not need to be tested.
- ^h On dosing days, vital signs should be completed predose (within 60 minutes prior to dosing), every 15 minutes during infusion, and 30–60 minutes postdose.

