4.3.3.1.1 Sensitivity Analysis Addressing the Effect of Missing Data After Treatment Discontinuation

Patients are expected to continue with study assessments after permanent treatment discontinuation. However, it is possible that patients who discontinue treatment fail to return for their follow-up assessments or discontinue the study, in which case some post-discontinuation data would be missing. Analysis under MAR will implicitly impute these missing values based on all observed data without distinguishing between on-treatment and off-treatment data and may therefore overestimate the treatment effect. Furthermore, the ICE strategy for treatment discontinuation would be a hybrid between a hypothetical and treatment policy strategy, and it becomes unclear what treatment effect is actually being estimated.

More conservative imputation approaches will be implemented to assess the sensitivity of treatment effect estimation and inference to missing data assumptions. The first approach will be to use conditional mean imputation for reference-based imputation of missing data ([Wolbers et al. 2022](#)). The imputation model will be an MMRM with baseline outcome, age, sex, height, treatment group, visit and treatment-by-visit interactions as covariates. Missing data for patients in the placebo arm will be imputed under MAR, and missing data for patients in the zinpentraxin alfa arm will be imputed under copy increments in reference. Under this reference-based assumption, patients in the intervention arm who discontinue treatment do not get any further benefit from treatment after discontinuation. The imputed, complete data will be analyzed via ANCOVA, with FVC (mL) slope as the outcome and baseline FVC, age, sex, height and treatment as covariates. Re-sampling based inference for the treatment effect estimate will be obtained via the jackknife.

In addition to the reference-based imputation, a tipping point analysis will be implemented by applying different delta-adjustments for each treatment group to the imputed data to see which combination of delta values tip the primary analysis result.

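### When a patient stops drug, the visit 4 weeks after the last dose can stand in for Week 52; a single Week 52 visit should be requested as well

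*Protocol*

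**What the plan says.** Continued attendance is the starting rule. Protocol 4.6 keeps patients who stop drug in the visit schedule, 4.6.1 says they are to be encouraged to attend through Week 52, and Appendix 1 footnote f widens their visit window to ±2 weeks. Section 3.1.1 is firmer: "Treated patients will be followed until the end of the 52-week study period unless the patient withdraws consent for follow-up or dies".

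The fallback, for a patient unable to return for the remaining visits, is in 4.6.1: "patients will return to the clinic for a treatment discontinuation visit 4 weeks after the final dose of study drug". The same paragraph directs the effort to collect spirometry, 6MWD, safety and survival data to the "time of the Week 52 or treatment discontinuation visit". Appendix 1 footnote d then closes follow-up: "Study discontinuation visit should occur 4 weeks after the treatment discontinuation visit (8 weeks after the final dose of study drug"). Section 4.6.2 repeats this timing, lists adverse event among the possible reasons for leaving the study, and lets the investigator withdraw a patient at any time. Patients who want no more assessments are invited to the extension study for survival follow-up only.

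SAP 1.1 applies a treatment-policy strategy to drug discontinuation and assumes that data missing afterwards are missing at random (MAR). The primary model (SAP 4.3.2) is a random-intercept, random-slope model, linear in time, with no term for being on or off drug. SAP 4.4.1 uses the same model for 6MWD.

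**The concern.** A patient who stops at Week 12 and is measured at Week 16 meets the letter of 4.6.1, even if one Week 52 visit would have been feasible. The treatment-policy estimand needs that Week 52 value. The exit visit is a poor substitute, because it falls 28 days after the last dose and Protocol 3.3.1 puts the tissue half-life of PTX-2 at 24–30 days. The data therefore stop at about the point where off-drug follow-up begins.

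For these patients the primary and key secondary models carry the on-drug slope to Week 52. SAP 4.3.3.1.1 says so itself: "Analysis under MAR will implicitly impute these missing values based on all observed data without distinguishing between on-treatment and off-treatment data". It adds that the effect may be overestimated and that it is then unclear which effect is being estimated. At stake are the size and meaning of the Week 52 estimates for FVC and 6MWD.

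**Working it through.** **1. The plan's own figure.** Protocol 6.2.1 states: "With a total of 658 patients (329 in each arm), the nominal power to detect a standardized effect size of 0.25" for FVC "using a two-sided type I error level of 0.05 is 0.89". With SD 403.5 mL, the SE is 403.5 × √(2/329) = 31.46 mL, and power is Φ(Δ/SE − 1.96).
- Δ = 0.25 × 403.5 = 100.9 mL gives Φ(3.21 − 1.96) = 0.894 (stated 0.89).
- Δ = 102 mL gives 0.900 (Table 7: 0.899).
- Δ = 89 mL gives 0.808 (Table 7: 0.806).

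The power figures reproduce and are not in dispute.

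**2. Variance components.** Protocol 6.2.1 gives SDs of change of 288.3 mL at Week 28 and 403.5 mL at Week 52. Under the planned model, Var(change at t) = σ_s²t² + 2σ_e².
- σ_s² = (403.5² − 288.3²)/(52² − 28²) = 79,695/1,920 = 41.5, so σ_s = 6.44 mL/week.
- σ_e² = (288.3² − 41.5 × 28²)/2 ≈ 25,287, so σ_e = 159 mL.
- The intercept SD is assumed to be 700 mL. Using 400 or 1000 mL does not change the bias.

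**3. The target.** Assumptions, none of them in the documents: a share d of each arm stops and is never measured after the exit visit; stops are spread evenly over Weeks 4, 8, …, 40 (mean 22); no benefit accrues after stopping. With on-drug effect D, the treatment-policy effect is D × [1 − d(1 − 22/52)]. For D = 102 mL and d = 10%, this is 102 × (1 − 0.1 × 30/52) = 96.1 mL.

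**4. What the planned model estimates.** This is the exact expectation of the generalized least squares treatment-by-time coefficient × 52, with 329 per arm, visits every 4 weeks, and leavers' data ending 4 weeks after the stop.

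| d | Target (mL) | Model (mL) | Overstatement (mL) | SE (mL) | Overstatement if all leavers give one Week 52 FVC (mL) |
|---|---|---|---|---|---|
| 5% | 99.1 | 101.8 | 2.7 | 28.5 | 0.4 |
| 10% | 96.1 | 101.5 | 5.4 | 28.9 | 0.8 |
| 20% | 90.2 | 101.0 | 10.8 | 29.7 | 1.6 |

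At 20%, if only half the leavers return at Week 52, 6.0 mL remains; if 30% return, 7.9 mL remains. If all return, the SE falls from 29.7 to 28.5 mL.

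**5. Cross-check by simulation.** Different inputs were used: residual SD 100 mL, baseline SD 750 mL, all stops at Week 24, nothing measured afterwards, D = 100.9 mL, 1000 replicates. The model mean was 101.1 against a target of 95.4 mL at 10%, and 100.5 against 90.0 mL at 20%. With every stopper followed at all visits it was 95.2 and 88.8 mL. With no treatment effect and 20% stopping in each arm, the mean estimate was 1.9 mL (Monte Carlo SE 1.5, 400 replicates), so no bias was seen.

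**The case against.** The strongest reply is that the protocol already wants these patients at Week 52. Attendance to Week 52 is the default in 3.1.1, 4.6 and 4.6.1, and the wider window serves it. The fallback is for patients unable to return for the remaining visits, and Week 52 is one of those, so a patient who can attend it is arguably not in the fallback group. Nothing says that missing intermediate visits ends participation, and the survival-only cohort is for patients who do not wish to continue assessments. All of that stands. A reader might infer that patients who stop drug are not asked back at Week 52, or that the Week 52 effect as a whole is extrapolated. The documents support neither: stoppers who keep attending contribute off-drug data, and the model uses them.

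The SAP also names the mechanism and plans copy-increments-in-reference imputation and a tipping-point analysis. Copy increments makes the same no-further-benefit assumption as the calculation here, so it is a relevant check. It is a sensitivity analysis, however, and leaves the primary estimate unchanged.

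The size is uncertain. The percentages are the share who stop and are never measured again, which is smaller than the share who stop. Any benefit persisting after stopping would shrink the bias. Patients described as unable to return may not come to one visit either.

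What survives is that the text makes the two visits alternatives and nowhere offers a single Week 52 visit.

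**Conclusion.** The point holds in limited form. For patients who leave through the fallback route, following the text can lose the off-drug Week 52 measurement that the estimand needs, and the primary and key secondary models fill the gap with the on-drug slope. Under the assumptions above, the overstatement of a 102 mL FVC effect is roughly 3 to 11 mL for 5% to 20% of patients never measured again: 0.19 SE at 10% (5.4/28.9) and 0.36 SE at 20% (10.8/29.7). The rate is the main unknown, and the documents do not supply it. No 6MWD figure was computed, though the model and the mechanism are the same.

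A reader might also infer a false-positive risk. That is not shown: with equal stopping and no true effect, no bias was seen. The issue is the size and interpretation of a real effect. Section 3.1.1, where only withdrawal of consent or death ends follow-up, and the wider exits in 4.6.2 need reconciling.

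**What to change.** - **4.6.1:** make the treatment discontinuation visit additional to Week 52 by replacing *or* with *and*. Ask every patient who has stopped drug and has not withdrawn consent to attend one Week 52 visit with spirometry and 6MWT, within the existing ±2-week window, even if intermediate visits are missed.
- **4.6.2 and Appendix 1 footnote d:** state that the visit 8 weeks after the last dose does not end follow-up for a patient willing to attend Week 52.
- **3.1.1 and 4.6.2:** reconcile the rules on what ends follow-up. Keep adverse event as a recorded reason for leaving; deleting it would retain nobody and lose information.
- **Reporting:** give, by arm, the number who stopped drug and the number of those with off-drug Week 52 data.

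The cost is a short amendment with matching consent wording and some site payments for a visit already in the schedule. Some patients will still not return, so the planned sensitivity analyses remain necessary.

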4.6.2 Patient Discontinuation from the Study

Patients will return to the clinic for a study completion or study discontinuation (end of study [*see week 56 of [Appendix 1](#)*]) visit 4 weeks after the treatment completion or treatment discontinuation visit (8 weeks after the final dose of study treatment).

Patients have the right to voluntarily withdraw from the study at any time for any reason. In addition, the investigator has the right to withdraw a patient from the study at any time.

Reasons for patient discontinuation from the study may include, but are not limited to, the following:

- Patient withdrawal of consent
- Study termination or site closure
- Adverse event
- Loss to follow-up

Every effort should be made to obtain a reason for patient discontinuation from the study. The primary reason for discontinuation from the study should be documented on the appropriate eCRF. If a patient requests to be withdrawn from the study, this request must be documented in the source documents and signed by the investigator. Patients who withdraw from the study will not be replaced.

Patients will be invited to enroll in the OLE study for long-term follow-up of survival data if the patient does not wish to continue with study treatments or other assessments and visits.

4.6.3 Study Discontinuation

The Sponsor has the right to terminate this study at any time. Reasons for terminating the study may include, but are not limited to, the following:

- The incidence or severity of adverse events in this or other studies indicates a potential health hazard to patients
- Patient enrollment is unsatisfactory

The Sponsor will notify the investigator if the Sponsor decides to discontinue the study.

4.6.4 Site Discontinuation

The Sponsor has the right to close a site at any time. Reasons for closing a site may include, but are not limited to, the following:

- Excessively slow recruitment
- Poor protocol adherence
- Inaccurate or incomplete data recording
- Non-compliance with the International Council for Harmonisation (ICH) guideline for Good Clinical Practice
- No study activity (i.e., all patients have completed the study and all obligations have been fulfilled)

5. ASSESSMENT OF SAFETY

PRM-151 is not approved, and clinical development is ongoing. The safety plan for patients in this study is based on clinical experience with PRM-151 in completed and

ongoing studies. The anticipated important safety risks for PRM-151 are outlined below. Please refer to the PRM-151 Investigator's Brochure for detailed safety information.

Several measures will be taken to ensure the safety of patients participating in this study. Eligibility criteria have been designed to exclude patients at higher risk for toxicities. Patients will undergo safety monitoring during the study, including assessment of the nature, frequency, and severity of adverse events. In addition, guidelines for managing adverse events, including criteria treatment interruption or discontinuation, are provided below.

If patients have been prescribed pirfenidone or nintedanib, this should comply with local prescribing information. Patients should adhere to the instructions and recommendations stated in the respective local labels. Investigators should consult local prescribing information for management of adverse events, including guidance on dose reductions and discontinuation of these treatments.

In exceptional circumstances, if patients cannot attend a study site for a scheduled visit, patients should be followed up ideally by telephone around the time of the scheduled visit to collect information on any adverse events and changes to concomitant medications.

Pandemic Preparedness

Patients with active infection are excluded from study participation. In the setting of a pandemic or epidemic, screening for infections prior to and during study participation should be considered according to local or institutional guidelines or those of applicable professional societies.

